2.4.4.2 Deaths

A listing of deaths will be provided. If there are more than 4 deaths in total, the following summaries of deaths will be generated for the safety population:

- N and % of patients who died by study period (on-study, treatment epoch for PAP or ETP, post-treatment epoch for PAP or ETP) and reasons for death.

- TEAEs leading to death (death as an outcome on the AE case report form page as reported by the Investigator) by primary SOC, and PT. Corresponding listing will be provided as well.

2.4.4.3 Analyses of laboratory variables

Observed measurements and changes from baseline to study time points in biochemistry, hematology, and urinalysis will be descriptively summarized for each visit or study assessment (baseline and each post-baseline time point), by study cohort and treatment arm, as well as by dose levels among avalglucosidase alfa treated patients for the overall avalglucosidase alfa treatment period. This section will be organized by biological functions.

All laboratory values will be classified as normal, above normal, or below normal based on normal ranges provided by the laboratory. The n and % of patients with the following selected laboratory abnormalities of all laboratory variables, when applicable, will be summarized for each visit or study assessment.

- Blood chemistry:
 - Plasma/serum electrolytes: sodium, potassium,
 - Liver function: AST, ALT, alkaline phosphatase, gamma-glutamyl transferase, total bilirubin, indirect bilirubin, direct bilirubin,
 - Renal function: creatinine,
 - Metabolic panel: glucose, albumin, protein, cholesterol, triglycerides,
 - Potential muscle toxicity: CK, CK with MB fraction,
 - Brain natriuretic peptide (BNP).
- Hematology: hemoglobin, white blood cell count with differential count (neutrophils, eosinophils, basophils, monocytes, and lymphocytes), platelets.

Comparisons of the worst laboratory abnormalities with the baseline will be presented for each laboratory parameter listed above, when applicable. This analysis will be conducted for PAP and for the overall avalglucosidase alfa treatment period.

Individual listings of patients with potentially clinically significant abnormalities will be presented.

The incidence of PCSAs (list provided in [Appendix B](#)) at any time during the treatment-emergent adverse event period will be summarized by biological functions and treatment groups. The PCSA analyses will be conducted for PAP primarily. Similar analyses will be conducted for the overall avalglucosidase alfa treatment period.

Drug-induced liver injury

The liver function tests, namely AST, ALT, alkaline phosphatase, and total bilirubin, are used to assess possible drug-induced liver toxicity. The following analyses will be performed:

- Time to onset of the initial ALT or AST elevation ($>3 \times \text{ULN}$) and total bilirubin elevation ($>2 \times \text{ULN}$), whichever comes first will be analyzed using Kaplan-Meier estimates by study cohort and treatment arm, if necessary.
- A graph of distribution of peak values of ALT versus peak values of total bilirubin (in logarithmic scale or in the scale of $\times \text{ULN}$ if appropriate) will also be presented. The graph will be divided into 4 quadrants with a vertical line corresponding to $3 \times \text{ULN}$ for ALT and a horizontal line corresponding to $2 \times \text{ULN}$ for total bilirubin, if necessary.
- Listing of possible Hy's law cases identified by study cohort and treatment arm (e.g., patients with any elevated $\text{ALT} > 3 \times \text{ULN}$, and associated with an increase in bilirubin $\geq 2 \times \text{ULN}$) with ALT, AST, alkaline phosphatase and total bilirubin, if necessary.
- Summary of the incidence of liver-related AEs by study cohort and treatment arm. The selection of preferred terms will be based on the hepatic disorder SMQ.

2.4.4.4 Analyses of vital sign variables

The summary statistics of all vital signs variables (central laboratory values and changes from baseline) will be calculated for each scheduled visit or study assessment (baseline, each post-baseline time point) by study cohort and treatment group.

The incidence of PCSAs (list provided in [Appendix B](#)) based on worst value at any time during the treatment-emergent adverse event period will be summarized by study cohort and treatment groups.

The PCSA analyses will be conducted for both PAP and ETP separately. Similar analyses will be conducted for the overall avalglucosidase alfa treatment period.

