- e Retrospective chart review at screening/baseline to collect available data on clinical decline or sub-optimal clinical response as outlined in [I 06](#) and [I 07](#).
- f Enrollment of patients in Cohorts 1 and 2 and randomization of patients in Cohort 3: IRT contact will be performed anytime during screening period for screening, prior to IMP administration for all other concerned visits and on or before Day 1 for enrollment/randomization.
- g Biweekly administration or, for alglucosidase alfa in Cohort 3 only, weekly administration (current stable dose). For all patients, all visits following V2 (Day 1) are calculated from the day of first infusion of investigational medicinal product (IMP) in 14-day increments with a window of \pm 7 days (in Cohort 3 participants, 7 day increments with a window of \pm 3 days for weekly (qw) alglucosidase alfa treatment) for infusions and safety assessments and \pm 14 days for all other assessments.
- h Female patients of childbearing potential only will have serum test for pregnancy at Screening, a urine β -hCG test up to 24 hours before D1 infusion and every 4 weeks thereafter.
- i Physical examination CRF will ask physician to record current muscle pain and cramps specifically at each PE assessment. Tanner stage will be assessed as part of the PE assessment at screening/baseline.
- j To be measured at screening/baseline, every 3 months up to Week 73 and then every 6 months until Week 145/EOS in all patients.
- k At every infusion. Vital signs include heart rate, systolic and diastolic blood pressure, respiratory rate, temperature, and oxygen saturation and are to be assessed prior to infusion, with each infusion rate change, at the end of the infusion and at the end of the post-infusion observation period. Collection windows are \pm 15 minutes.
- l 12-lead ECG after at least 15 minutes in supine position (if supine is feasible for the patient). Review should be done at the site in a timely manner to determine if there are any safety concerns and for clinical management of the patient. In addition, reading will be done by central reader for analyses purposes only.
- m 12-lead ECG after at least 15 minutes in supine position (in triplicate predose at Day 1 only) and prior to receiving IMP: 3 ECGs within 5 minutes will be performed with at least 1 minute between 2 replicates.
- n Biochemistry panel will include BNP and CK.

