The benefits and risks assessment of avalglucosidase alfa for the Phase 2 ACT14132 study is based upon the nonclinical studies of avalglucosidase alfa in GAA knockout mice, CD 1 mice and cynomolgus monkey studies, as well as on the results from the clinical Phase 1/2 TDR12857 study (in adult treatment-naïve late-onset Pompe disease [LOPD] patients and adult LOPD patients who had been treated with alglucosidase alfa prior to their study participation) and previous experience with alglucosidase alfa. In nonclinical studies, avalglucosidase alfa was more successful in reducing glycogen in muscle tissue compared to alglucosidase alfa. The safety profile of avalglucosidase alfa in both nonclinical and clinical studies has shown avalglucosidase alfa to be well tolerated; adverse events (AEs) and infusion-associated reactions (IARs) are mostly nonserious and usually manageable (see IB Section 7 for detailed discussion of risks). The potential benefits of avalglucosidase alfa, balanced against its known risks, support further investigation of the safety and efficacy of avalglucosidase alfa across the broad spectrum of Pompe disease, including both pediatric and adult patients.

A risk of acute cardiorespiratory failure requiring intubation and inotropic support after infusion in IOPD patients with underlying cardiac hypertrophy is considered based on experience with alglucosidase alfa and due to fluid overload. Appropriate medical support and monitoring measures should be readily available during avalglucosidase alfa infusion, and infants with cardiac dysfunction may require prolonged observation times that should be individualized based on the needs of the patient. Caution should be taken with fluid volume infusion.

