11.4.2.3 Physical examination, vital signs, and electrocardiogram

Potentially clinically significant findings observed during the on-treatment period for vital signs (including but not limited to blood pressure, heart rate, respiratory rate, etc) and ECG (QTc, PR interval, etc) will be summarized by study cohort and treatment group, as well as by dose levels among avalglucosidase alfa-treated patients. Listings of abnormal findings/values from these data as well as from PE assessment inclusive of body weight and height, as well as head circumference and Tanner stage, will be presented.

11.4.2.4 Anti-avalglucosidase alfa and anti-alglucosidase alfa antibodies, neutralizing antibodies, and other immunogenicity testing

Percentage of patients who seroconverted to avalglucosidase alfa, time to seroconversion and peak anti-avalglucosidase alfa antibody titer will be summarized using summary statistics.

Anti-avalglucosidase alfa and anti-alglucosidase alfa antibody titer values will be summarized using summary statistics at each study visit. All data will be presented in listings for each patient.

By patient listings will also display results of neutralizing antibody, circulating immune complex, anti-avalglucosidase alfa IgE antibody, serum tryptase activity, complement activation, and skin testing performed. Descriptive summaries may also be provided as appropriate.

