2.1.3.3 Laboratory safety variables

The clinical laboratory data consist of blood analysis (including hematology and biochemistry) and urinalysis. Clinical laboratory values after conversion into standard international units will be analyzed, and international units will be used in all listings and tables.

Blood samples for clinical laboratories will be taken as specified in the study protocol. The laboratory parameters will be classified as follows:

- Hematology: red blood cell count, hematocrit, hemoglobin, white blood cell count with differential count (neutrophils, eosinophils, basophils, monocytes, and lymphocytes), platelets.
- Biochemistry:
 - Plasma/serum electrolytes: sodium, potassium, chloride, calcium;

- Liver function: AST, ALT, alkaline phosphatase, gamma-glutamyl transferase, total and direct bilirubin;
- Renal function: creatinine, blood urea nitrogen, uric acid;
- Metabolic panel: glucose, albumin, total proteins, total cholesterol, triglycerides;
- Potential muscle toxicity: CK, CK with MB fraction, lactate dehydrogenase;
- Brain natriuretic peptide (BNP).
- Urinalysis will include urine color, appearance, specific gravity, proteins, glucose, erythrocytes, leukocytes, ketone bodies, and pH to be assessed:
 - Qualitatively: A dipstick is to be performed on a freshly voided specimen for qualitative detection using a reagent strip;
 - Quantitatively: A quantitative measurement for protein, erythrocytes, and leukocytes count will be required in the event that the urine sample test is positive for any of the above parameters by urine dipstick (e.g., to confirm any positive dipstick parameter by a quantitative measurement).

2.1.3.4 *Vital signs*

Vital signs include heart rate, systolic and diastolic blood pressure, respiratory rate, temperature, and oxygen saturation.

2.1.3.5 *Electrocardiogram variables*

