2.4.4 Analyses of safety data

In general, for PAP, the summary of safety results will be presented by study cohort and treatment arm. For the overall avalglucosidase alfa treatment period, the summary of safety results will be presented by initial planned dose levels among avalglucosidase alfa patients. For Cohort 3 alglucosidase alfa patients, the summary of safety results for ETP will be presented in separate tables.

In the PAP analysis, the safety analyses will be carried out with patients by the actual treatment received, irrespective of the treatment the patient has been randomized to. The actual treatment received is defined as:

- avalglucosidase alfa if the patient receives at least one infusion with this drug in PAP;
- alglucosidase alfa if the patient only receives alglucosidase alfa in PAP.

In the ETP analysis and/or overall evaluation of avalglucosidase alfa safety, the safety analyses will be carried out by the following 3 groups:

- AVAL/AVAL in ETP includes data in ETP among patients who received avalglucosidase alfa in PAP and ETP;
- ALGLU/AVAL in ETP includes data in ETP among patients who received alglucosidase alfa in PAP and received avalglucosidase alfa in ETP;
- AVAL/AVAL and ALGLU/AVAL in overall avalglucosidase alfa treatment period includes data in PAP and/or ETP among patients who received avalglucosidase alfa in that period.

General rules

All safety analyses will be performed on the safety population as defined in [Section 2.3.1](#), unless otherwise specified, using the following common rules:

- The safety baseline value is defined the same as the baseline definition in [Section 2.1.1](#).
- The potentially clinically significant abnormality (PCSA) values are defined as abnormal values considered medically important by the Sponsor according to predefined criteria/thresholds based on literature review and defined by the Sponsor for clinical laboratory tests, vital signs, and ECG (PCSA version dated January 2014 [[Appendix B](#)]).
 - PCSA criteria will determine which patients had at least 1 PCSA during the treatment epoch (for PAP and ETP respectively), taking into account all evaluations performed during this period, including nonscheduled or repeated evaluations.
 - The number of all such patients will be the numerator for the on-treatment PCSA percentage; the denominator will be the number of patients assessed for that given parameter in the treatment epoch by treatment group on the safety population.

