Heart rate	≤ 50 bpm and decrease from baseline ≥ 20 bpm ≥ 120 bpm and increase from baseline ≥ 20 bpm	Birth/0 to 27 days old (Neonates) ≤ 90 bpm and decrease from baseline ≥ 20 bpm ≥ 190 bpm and increase from baseline ≥ 20 bpm 28 days/1 month to 23 months old (Infants) ≤ 80 bpm and decrease from baseline ≥ 20 bpm ≥ 175 bpm and increase from baseline ≥ 20 bpm 24 months/2 years to <6 years old (Children) ≤ 75 bpm and decrease from baseline ≥ 20 bpm ≥ 140 bpm and increase from baseline ≥ 20 bpm 6 to <12 years old (Children) ≤ 50 bpm and decrease from baseline ≥ 20 bpm ≥ 120 bpm and increase from baseline ≥ 20 bpm 12 to 16/18 years old (Adolescents) ≤ 50 bpm and decrease from baseline ≥ 20 bpm ≥ 120 bpm and increase from baseline ≥ 20 bpm
Systolic BP	≤ 95 mmHg and decrease from baseline ≥ 20 mmHg ≥ 160 mmHg and increase from baseline ≥ 20 mmHg	Birth/0 to 27 days old (Neonates) ≤ 60 mmHg and decrease from baseline ≥ 20 mmHg ≥ 85 mmHg and increase from baseline ≥ 20 mmHg 28 days/1 month to 23 months old (Infants) ≤ 70 mmHg and decrease from baseline ≥ 20 mmHg ≥ 98 mmHg and increase from baseline ≥ 20 mmHg 24 months/2 years to <6 years old (Children) ≤ 70 mmHg and decrease from baseline ≥ 20 mmHg ≥ 101 mmHg and increase from baseline ≥ 20 mmHg 6 to <12 years old (Children) ≤ 80 mmHg and decrease from baseline ≥ 20 mmHg ≥ 108 mmHg and increase from baseline ≥ 20 mmHg 12 to 16/18 years old (Adolescents) ≤ 90 mmHg and decrease from baseline ≥ 20 mmHg ≥ 119 mmHg and increase from baseline ≥ 20 mmHg

Diastolic BP	≤ 45 mmHg and decrease from baseline ≥ 10 mmHg ≥ 110 mmHg and increase from baseline ≥ 10 mmHg	Birth/0 to 27 days old (Neonates) ≤ 34 mmHg and decrease from baseline ≥ 10 mmHg ≥ 50 mmHg and increase from baseline ≥ 10 mmHg 28 days/1 month to 23 months old (Infants) ≤ 34 mmHg and decrease from baseline ≥ 10 mmHg ≥ 54 mmHg and increase from baseline ≥ 10 mmHg 24 months/2 years to <6 years old (Children) ≤ 34 mmHg and decrease from baseline ≥ 10 mmHg ≥ 59 mmHg and increase from baseline ≥ 10 mmHg 6 to <12 years old (Children) ≤ 48 mmHg and decrease from baseline ≥ 10 mmHg ≥ 72 mmHg and increase from baseline ≥ 10 mmHg 12 to 16/18 years old (Adolescents) ≤ 54 mmHg and decrease from baseline ≥ 10 mmHg ≥ 78 mmHg and increase from baseline ≥ 10 mmHg
--------------	---	--

Signature Page for VV-CLIN-0258347 v2.0
act14132-16-1-9-sap

Approve & eSign

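### Protocol 11.4.2.3 commits to summarising clinically significant vital-sign findings and names respiratory rate, but SAP Appendix B sets limits for only 3 of the 6 vital signs collected, and the departure is not declared

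*SAP*

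**What the plan says.** The protocol's flow chart footnote on vital signs (section 1.2.1) reads "At every infusion. Vital signs include heart rate, systolic and diastolic blood pressure, respiratory rate, temperature, and oxygen saturation". Protocol 9.1.1.3 sets the reading times: before the infusion, at each rate change (the start counts as the first), at the end of infusion, and at the end of the observation period. SAP 2.1.3.4 defines the same six variables. Vital sign measurements are listed under the primary endpoint in the protocol summary.

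The analysis commitment is in Protocol 11.4.2.3: "Potentially clinically significant findings observed during the on-treatment period for vital signs (including but not limited to blood pressure, heart rate, respiratory rate, etc". These findings are to be summarised by cohort and treatment group, and by dose level among avalglucosidase alfa patients. The same section says that abnormal values from these data will be listed.

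SAP 2.4.4 makes the definition of abnormal depend on criteria "defined by the Sponsor for clinical laboratory tests, vital signs, and ECG (PCSA version dated January 2014", reproduced in Appendix B. SAP 2.4.4.4 then says that the incidence of abnormalities on that list "based on worst value at any time during the treatment-emergent adverse event period will be summarized by study cohort and treatment groups". The vital-sign block of Appendix B opens with heart rate (adult low limit "≤ 50 bpm and decrease from baseline ≥ 20 bpm", then five paediatric age bands), continues with systolic and diastolic blood pressure, and ends there.

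**The concern.** A table of potentially clinically significant abnormalities (PCSAs) can be produced only for a variable that has a limit. With no limit for respiratory rate, oxygen saturation or temperature, the SAP cannot deliver the patient count that the protocol commits to. For respiratory rate, which the protocol names, the shortfall is explicit.

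The gap lies in the primary safety endpoint of a small open-label trial. A PCSA count works from the recorded value and does not depend on an investigator deciding that the reading was an adverse event. Protocol section 4 also states: "A risk of acute cardiorespiratory failure requiring intubation and inotropic support after infusion in IOPD patients with underlying cardiac hypertrophy is considered". That respiratory rate and saturation bear on this risk is an inference, since the documents do not say so, but it is a reasonable one and makes these two signs awkward ones to leave out.

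**Working it through.** No formula in the plan is at issue. The check sets what is collected against what is promised and what can be counted.

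| Vital sign | Collected at every infusion (Protocol 9.1.1.3, SAP 2.1.3.4) | Named in Protocol 11.4.2.3 | Limit in SAP Appendix B | PCSA count possible |
|---|---|---|---|---|
| Heart rate | yes | yes | yes | yes |
| Systolic BP | yes | yes, as blood pressure | yes | yes |
| Diastolic BP | yes | yes, as blood pressure | yes | yes |
| Respiratory rate | yes | yes | no | no |
| Oxygen saturation | yes | no; open wording only | no | no |
| Temperature | yes | no; open wording only | no | no |

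Coverage: 3 of 6 collected signs have a limit and 6 − 3 = 3 have none. Of the three signs that the protocol names (blood pressure, heart rate, respiratory rate), one has none.

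**Where a reading of an uncovered sign goes**

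1. *Scheduled reading.* SAP 2.4.4.4 gives by-visit summary statistics for all vital-sign variables, as values and as changes from baseline. SAP 2.4 requires these to include at least minimum and maximum. An extreme scheduled value therefore appears as the minimum or maximum for that visit.
2. *Unscheduled reading.* SAP 2.5.5 keeps unscheduled vital signs out of the by-visit summaries and uses them for baseline, worst values and PCSA summaries. In 2.4.4.4 the worst value is used only through the PCSA table. For these three signs that table does not exist, so an unscheduled reading enters no planned vital-sign table unless it serves as the baseline.
3. *Worst value per patient.* None is tabulated. On every-other-week dosing a child has 13 planned infusions in the primary period with at least 4 reading times each: 13 × 4 = 52 or more scheduled readings of each sign. By-visit minima and maxima spread these over many rows and do not say how many different children had an abnormal value.
4. *Listing.* SAP 2.4.4.3 lists patients with laboratory PCSAs, 2.4.4.5 lists ECG measurements, and 2.4.4.6 lists physical examination variables. Section 2.4.4.4 specifies no listing.

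**Is the departure declared?** SAP 1.5, on changes to the protocol's statistical section, does not mention vital signs. SAP 1.6 says only that the PCSA list was updated to follow the ISS, and does not say that the protocol's commitment has been narrowed.

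**The case against.** The case on the other side has five parts, and much of it stands.

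- A reader might infer that one child's desaturation would vanish into a group mean. The documents do not support that: minimum and maximum are required, and in groups of about 5 a scheduled extreme would be visible.
- A reader might also infer that harm would be seen only if reported as an adverse event. That fails for the same reason. In addition, the protocol's promise to list abnormal values has not been withdrawn; the SAP merely omits it. What remains is that a listing of abnormal values needs a definition of abnormal, and three signs have none.
- The named risk is largely captured elsewhere. New invasive ventilatory support is a medically important serious event (Protocol 10.4.1.2). Vital-sign abnormalities that are symptomatic, need treatment or consultation, change dosing or are serious must be recorded as adverse events (10.4.2). SAP 2.4.4.1 tabulates events regardless of relationship, and infusion-associated reactions by timing relative to infusion. What can escape the adverse event tables is mainly an asymptomatic, untreated, non-serious change. This stands, and it limits the stakes.
- The protocol does not name oxygen saturation or temperature in 11.4.2.3, and 11.4.2 leaves the criteria to the sponsor. This stands: the explicit breach concerns respiratory rate alone.
- A reader might want a cardiorespiratory failure grouping beside the hypersensitivity and hepatic ones. No document promises it, so its absence is not a departure.

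None of this supplies the missing patient count, brings in the unscheduled readings, or explains why a sign named in the protocol has no limit.

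**Conclusion.** The point holds as a gap between protocol and SAP in the primary safety analysis. Followed as written, the SAP yields no patient-level worst-value count for 3 of 6 vital signs. For respiratory rate this contradicts an explicit commitment; for oxygen saturation and temperature it falls short of the protocol's open-ended wording combined with its own definition of vital signs. Unscheduled readings of these signs have no place in the planned vital-sign tables beyond the baseline derivation, and the vital-sign listing is missing from the SAP without explanation.

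The size is moderate. What is lost is a count of patients, the unscheduled readings and a specified listing. Scheduled extremes and reportable events remain visible, so the documents do not support saying that cardiorespiratory harm would go undetected.

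Two assumptions: the vital-sign block of Appendix B is complete as published (the signature page follows diastolic blood pressure directly), and no separate programming document adds limits for the three signs.

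**What to change.** Before database lock:

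1. Add respiratory rate, oxygen saturation and temperature to the vital-sign block of Appendix B, with analysis limits set by the sponsor. Respiratory rate can use the age bands already used there for heart rate. The documents give no thresholds, and none is proposed here.
2. In SAP 2.4.4.4, tabulate the number of patients meeting each limit on worst on-treatment value, with unscheduled readings included as SAP 2.4.4 and 2.5.5 already provide.
3. Restore in 2.4.4.4 the by-patient listing of abnormal vital signs that Protocol 11.4.2.3 promises.

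If the sponsor decides against limits for any of these signs, SAP 1.5 or 1.6 should say so and give the reason.

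The cost is SAP wording, a few table rows and one listing, all from data already collected. These are reporting limits only: they change no monitoring, dosing or other clinical rule.
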